#### **4.6 REPLACEMENT OF SUBJECTS**

Enrolled subjects will not be replaced.

## 5. INVESTIGATIONAL MEDICINAL PRODUCT INFORMATION

ZX008 will be administered in the current study. A brief description of the ZX008 product is provided below (Table 4).

**Table 4. Investigational Medicinal Product – ZX008**

	Study Product
Substance Code	ZX008
Active Substance (INN)	Fenfluramine Hydrochloride
Trade Name	Not applicable
Formulation (including dosage form and strength)	Solution 2.5 mg/mL
Route/Mode of Administration	Oral
Manufacturer	PCI Pharma Services on behalf of Zogenix International Limited

### 5.1 IDENTITY OF INVESTIGATIONAL MEDICINAL PRODUCT

ZX008 drug product is an oral aqueous solution of fenfluramine hydrochloride buffered to pH 5 and provided in a concentration of 2.5 mg/mL. The excipients selected have been approved for use in the formulations of currently marketed drug products and are considered to be safe. The solution formulation will be suitably flavored, and will contain preservatives and a thickening agent. The product is sugar free and is intended to be compatible with a ketogenic diet (KD). The formulation will be provided in bottles with tamper-evident, child-resistant caps.

Doses to be studied include 0.2 mg/kg/day, 0.4 mg/kg/day, 0.6 mg/kg/day, and 0.8 mg/kg/day divided into two daily doses, up to a maximum of 30 mg/day. If the parent/caregiver is unable to administer the full dose due to spillage (eg, dose was spilled during measuring, subject spit dose out during administration), he/she should attempt to give the full dose noting the extra amount used to fulfil the dose. **Care must be taken not to overdose.** If the amount spilled is not known, the parent/caregiver should not give additional medication to avoid potential overdose.

#### 5.1.1 Labeling and Packaging

The ZX008 product will be packaged and labeled according to current ICH, Good Manufacturing Practices (GMP), and GCP guidelines, and national legal requirements.

Dosing directions for the product can be found in the IMP handling instructions for the study subjects and for the investigator.

## 5.2 DESCRIPTION OF REFERENCE TREATMENT, COMPARATOR, AND/OR PLACEBO

No comparators, reference treatments, or placebo will be used in this study.

## 5.3 IMP ACCOUNTABILITY

The investigator or delegate will confirm receipt of all shipments of the IMP in writing using the receipt form(s) provided by the Sponsor or vendor.

Assignment of ZX008 bottles to the subject will be handled through an interactive voice response (IVR) or Interactive Web Response (IWR) platform. The investigator or delegate will be required to register the subject through IVR/IWR and all study medication will be assigned to the subject through the IVR/IWR. The IVR/IWR will also maintain a log of all received and dispensed medication.

All supplies must be accounted for throughout the study using the drug accountability form provided by the Sponsor before the start of the study. At the end of the study, the dated and signed (by the investigator or delegate, eg, pharmacist) original drug accountability form must be retained at the study site as verification of final drug accountability.

Records for the delivery of the IMP to the study site, the inventory at the study site, the use by each subject (use by subject will be documented in the subject diary), and the destruction or return of the IMP to the Sponsor must be maintained by the investigator (or delegate). The records will include dates, quantities, batch numbers, and unique code numbers assigned to the IMP and to the subjects. The investigator must maintain records documenting that subjects were provided with the doses of the IMP specified in this study protocol. Furthermore, the investigator must reconcile all IMPs received from the Sponsor. The investigator must provide reasons for any discrepancies in drug accountability. Forms will be provided by the Sponsor to ensure standardized and complete drug accountability.

## 5.4 TREATMENT ADMINISTRATION

### 5.4.1 OLE Treatment Period

The investigator (or delegate) will dispense IMP only to subjects included in this study following the procedures set out in this study protocol.

Study medication will be administered as equal doses BID in the morning and in the evening, approximately 12 hours apart, with food. Each dose should be separated by a minimum of 8 hours and a maximum of 12 hours. A missed dose of study medication may be taken later up to 8 hours before the next scheduled dose; otherwise, the missed dose should not be given. Administration of the initial IMP will be based on the 0.2 mg/kg/day (maximum 30 mg/day or

20 mg/day for subjects taking concomitant STP) dose and subject's weight at Visit 1 (Study Day 1). At Visits 5 to 15 (Months 3 to 33), if the subject's weight has changed  $\pm 25\%$  of the weight from the previous dose calculation, the IMP dose will be recalculated. Subjects will be dosed using the oral dosing syringe provided.

During the OLE Treatment Period, all subjects will be treated initially with 0.2 mg/kg/day for 1 month to assess effectiveness of this dose in all study subjects. After 1 month at a dose of ZX008 0.2 mg/kg/day, the investigator may adjust the dose of each subject based on effectiveness and tolerability.

Dose changes should be made in increments of 0.2 mg/kg/day, as follows:

- Subjects who are not receiving concomitant STP: may increase to a maximum of 0.8 mg/kg/day but not to exceed total dose of 30 mg/day
- Subjects who are receiving concomitant STP: the first dose change will be to 0.4 mg/kg/day and the final dose change will be to 0.5 mg/kg/day, but not to exceed 20 mg/day

Dose increases should not occur earlier than every 14 days at each dose level. Dose increases may only occur after a review of the diary and reported AEs, and if, in the investigator's opinion, seizure frequency, severity, and/or duration indicates a change in medication regimen is warranted. Dose decreases for tolerability can occur at the investigator's discretion, in dose amounts and frequency appropriate for the situation. ZX008 dose adjustments outside of these parameters should be discussed with the Medical Monitor prior to initiation.

If after approximately the midway point of the first 30 days on ZX008 0.2 mg/kg/day there is a clinically meaningful worsening in seizure type, frequency, and/or duration compared with the recent treatment in the core study, the investigator, in consultation with the Medical Monitor, may increase the dose to 0.4 mg/kg/day (maximum 30 mg/day for subjects who are not receiving concomitant STP; 20 mg/day for subjects who are receiving concomitant STP). A clinically meaningful worsening would be an increase in frequency, severity or duration of existing seizures, or emergence of a new seizure type. The description of clinical worsening must be documented in the source notes and case report form (CRF). Further increase to 0.8 mg/kg/day (maximum 30 mg/day) for subjects who are not receiving concomitant STP, and to 0.5 mg/kg/day (maximum: 20 mg/day) for subjects who are receiving concomitant STP could also be undertaken for the same conditions after a minimum of 4 days on 0.4 mg/kg/day, if the condition has not stabilized on the 0.4 mg/kg/day dose; however, the maximal dose determined for subjects on concomitant STP must not be exceeded. Dosing outside of the specified range (ie, 0.2 to 0.8 mg/kg/day or 0.5 mg/kg/day for subjects taking concomitant STP) may be considered after consultation between the investigator and Medical Monitor.

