### 5.4.2.1 Taper Period for Subjects not Receiving Concomitant STP

The tapering scheme is a 2-step process for subjects who are not receiving concomitant STP, including subjects from core studies ZX008-1501 and ZX008-1502, and from study ZX008-1504 Cohort 1/Regimens 1&2. This is described in [Table 5](#).

Study medication will be administered as equal doses BID in the morning and in the evening, approximately 12 hours apart, with food. Each dose should be separated by a minimum of 8 hours and a maximum of 12 hours. A missed dose of study medication may be taken later up to 8 hours before the next scheduled dose; otherwise, the missed dose should not be given. IMP will be administered using the oral dosing syringe provided.

**Table 5. Taper Algorithm for Subjects from Core Studies ZX008-1501, ZX008-1502, and ZX008-1504 Cohort 1/Regimens 1&2 Not Receiving Concomitant STP**

Current Dose	Taper Step 1 Days 1-4 after study completion or early termination	Taper Step 2 Days 5-8 after study completion or early termination
ZX008 0.2 mg/kg/day	Not applicable	Not applicable
ZX008 0.4 mg/kg/day	ZX008 0.2 mg/kg/day	Not applicable
ZX008 0.6 mg/kg/day	ZX008 0.4 mg/kg/day	ZX008 0.2 mg/kg/day
ZX008 0.8 mg/kg/day	ZX008 0.4 mg/kg/day	ZX008 0.2 mg/kg/day

Note: maximum daily dose of ZX008 is 30 mg.

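### The twice-daily dosing interval rule can be met only at exactly 12 hours, and the missed-dose rule beside it permits gaps of up to 16 hours

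*Protocol*

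**What the plan says.** Protocol section 5.4.1 gives three timing statements in succession.

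- Spacing: "Study medication will be administered as equal doses BID in the morning and in the evening, approximately 12 hours apart, with food".
- Interval: "Each dose should be separated by a minimum of 8 hours and a maximum of 12 hours".
- Missed dose: "A missed dose of study medication may be taken later up to 8 hours before the next scheduled dose". After that point the dose is omitted.

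Sections 5.4.2.1 and 5.4.2.2 repeat all three for the taper, for subjects without and with concomitant stiripentol respectively. In 5.4.2.1, for example, the interval limit and the missed-dose allowance again stand next to each other: "hours and a maximum of 12 hours. A missed dose of study medication may be taken later up to 8 hours before the next scheduled". Nothing in the protocol limits the 8-to-12-hour range to the daytime gap, and nothing exempts a late or omitted dose from the 12-hour maximum.

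**The concern.** The interval sentence reads like a tolerance band around the nominal 12-hour spacing. A band for twice-daily dosing has to extend on both sides of 12, because shortening one gap lengthens the other by the same amount. This one extends only downwards. The missed-dose sentence then allows timing that the interval sentence rules out.

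What is at stake is practical. Caregivers give this drug at home for up to 36 months. When a dose is late, one sentence allows it and the sentence before it disallows the gap that results. Two sites could judge the same late dose differently, and each could point to the protocol.

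**Working it through.** **Inputs, all from section 5.4.1 and repeated in 5.4.2.1 and 5.4.2.2**

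- Two doses per 24 hours, nominally about 12 hours apart.
- Gap between doses: minimum 8 hours, maximum 12 hours.
- A late dose is allowed until 8 hours before the next scheduled dose. After that it is omitted.

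**Step 1: can the stated 8-to-12-hour range be realised?** Let *a* be the morning-to-evening gap and *b* the evening-to-morning gap on a repeating schedule.

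- *a* + *b* = 24
- *b* ≤ 12 gives *a* = 24 − *b* ≥ 12
- together with *a* ≤ 12, this gives *a* = 12 and *b* = 12

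A search over all values of *a* from 0 to 24 hours in 5-minute steps found 12.0 as the only one meeting both limits. Individual cases:

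| First gap (h) | Second gap (h) | Both within 8–12? |
|---|---|---|
| 8 | 16 | No |
| 9 | 15 | No |
| 10 | 14 | No |
| 11 | 13 | No |
| 12 | 12 | Yes |
| 12.5 | 11.5 | No |

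The stated range therefore collapses to a single point. On a regular schedule the 8-hour minimum never comes into play, and the approximate spacing in the first sentence has no room on the long side.

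**Step 2: the missed-dose rule against the maximum.** Put the previous dose at hour 0, the missed dose at hour 12 and the next scheduled dose at hour 24.

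- Latest permitted late dose: 24 − 8 = hour 16
- Gap from the previous dose: 16 − 0 = 16 hours
- Excess over the stated maximum: 16 − 12 = 4 hours
- Gap to the next scheduled dose: 24 − 16 = 8 hours, which meets the minimum

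On a clock with doses at 08:00 and 20:00, a missed 08:00 dose may be given until 12:00, which is 16 hours after the 20:00 dose. If the dose is omitted instead, the gap between doses taken is 24 hours.

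**Step 3: where the text agrees and where it does not.** The 8-hour minimum on its own implies gaps of 8 to 16 hours (24 − 8 = 16), which is the range the missed-dose rule produces. The minimum and the missed-dose cut-off are thus consistent with each other. The 12-hour maximum is what conflicts with both.

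**The case against.** Four points can be made on the other side.

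**The wording is soft.** The spacing is only approximate, and the interval sentence says should, not must. That stands as far as it goes: a gap above 12 hours departs from the stated interval but is not a defined protocol deviation. It does not make the sentences agree.

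**A sensible reading exists.** The range might describe the time from a dose, taken on time or late, to the next scheduled dose. That time runs from 12 hours down to 8, and on this reading the minimum does some work. The missed-dose sentence might also be read as a specific exception to the general interval. Alternatively, the range might apply only to the daytime gap, leaving 12 to 16 hours overnight. None of these limits is written down; the text speaks of each dose. The forward reading still leaves a late dose more than 12 hours after the preceding one. The daytime reading fails for a late evening dose: due at 20:00 and allowed until 00:00, it can fall 16 hours after the 08:00 dose.

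**Caregivers may be told something clearer.** Section 5.1.1 refers to separate handling instructions, which are not available here. They may resolve the matter in practice, but the protocol would still contradict itself.

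**The consequences may be slight.** This largely stands. A reader might infer that almost every dosing day becomes a deviation, which then counts against compliance, leads to withdrawal or removes subjects from the Per Protocol Population. The documents do not support that chain:

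- Section 5.7 monitors compliance through returned volume, the dispensation log and diary entries on dose, dosing frequency and consumption. It does not list clock times or gaps.
- Section 4.4 item 5 concerns ongoing or repeated noncompliance, and the list applies at the discretion of the sponsor or investigator.
- Section 10.2.3 excludes subjects for major deviations with a significant effect on clinical outcome. A gap slightly over 12 hours is unlikely to qualify.
- Section 11.4 asks for notable deviations to be reported and does not name dosing gaps.

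**Conclusion.** The interval rule is wrong as written in all three sections. Taken literally, it admits only exact 12/12 dosing, and the adjacent missed-dose rule permits a gap up to 4 hours beyond its maximum. This rests on two things: the two gaps on a repeating twice-daily schedule add up to 24 hours, and the limits apply to every gap, as the text says. No assumption about how precisely caregivers time doses is needed.

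The defect concerns the clarity of an operative dosing instruction. Its effect is that a late dose cannot be classified consistently as inside or outside the schedule. No endpoint, sample size, power or significance level rests on it, and no effect on Per Protocol membership is shown. It merits correction because it sits in the core administration text, appears three times and is cheap to repair.

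**What to change.** The sponsor's clinical team should reconcile the spacing, interval and missed-dose sentences in sections 5.4.1, 5.4.2.1 and 5.4.2.2 into one rule. That rule should be one that both daily gaps and the missed-dose allowance can satisfy together, and it should say which gaps it covers and how late doses stand in relation to it. The handling instructions named in section 5.1.1 should be checked and brought into line. The values are a clinical decision, and none is suggested here.

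The cost is a short wording change repeated in three sections, plus a check of the dosing instructions. No analysis changes.

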If after approximately the midway point of the first 30 days on ZX008 0.2 mg/kg/day there is a clinically meaningful worsening in seizure type, frequency, and/or duration, compared with the recent treatment in the core study, the investigator, in consultation with the medical monitor, may increase the dose to 0.4 mg/kg/day (maximum 30 mg/day for subjects who are not receiving concomitant STP; 20 mg/day for subjects who are receiving concomitant STP). A clinically meaningful worsening would be an increase in frequency, severity or duration of existing seizures, or emergence of a new seizure type. The description of clinical worsening must be documented in the source notes and case report form (CRF). Further increase to 0.8 mg/kg/day (maximum 30 mg/day) for subjects who are not receiving concomitant STP, and to 0.5 mg/kg/day (maximum 20 mg/day) for subjects who are receiving concomitant STP could also be undertaken for the same conditions after a minimum of 4 days on 0.4 mg/kg/day, if the condition has not stabilized on the 0.4 mg/kg/day dose. Dosing outside of the specified range (ie, 0.2 to 0.8 mg/kg/day) may be considered after consultation between the investigator and Medical Monitor.

A follow-up electrocardiogram (ECG) and echocardiogram (ECHO) will be performed at 3 and 6 months after study drug discontinuation for early termination and for those subjects who complete the study. Caregivers will use a diary daily to record the number/type of seizures, dosing, and use of rescue medication. A schedule of assessments is provided in **Table 1** for subjects from core studies ZX008-1501 and ZX008-1502 and those who did not participate in one of the core studies (de novo subjects), and in **Table 2** for subjects from core study ZX008-1504.

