#### 1.4 PRECLINICAL DATA

The pharmacokinetics (PK) of fenfluramine, norfenfluramine and their respective isomers has been studied in mice, rats, dogs and humans. The PK in humans differs from that of other species, with a longer duration of exposure to both the parent and the metabolite. In vitro metabolism studies have shown that there are large species differences in PK and metabolism of fenfluramine after oral administration. A 10-week GLP juvenile toxicology and toxicokinetic study in rats, which included fenfluramine hydrochloride doses of 3.5, 9 and 20 mg/kg/day by

oral gavage for 10 weeks (Days 7 to 76 postpartum). The data from the juvenile toxicology studies suggest that the effects of fenfluramine in juvenile animals (CNS-related clinical signs, effects on body weight and food consumption, and neurobehavioral deficits) are similar to effects previously reported in neonatal and adult rats (ZX008 IB). There was no evidence of CNS-related histopathology findings.; Importantly, there were also no histopathologic findings in aortic or mitral cardiac valves, and no adverse effects on any other tissues at necropsy.

The NOAEL for the juvenile rats was determined to be 9 mg/kg/day. A NOAEL of 9 mg/kg/day corresponds to PND 76 AUC0-t of 3480 hr\*ng/mL for males and 4680 hr\*ng/mL for females for fenfluramine, and 4470 hr\*ng/mL for males and 6210 hr\*ng/mL for females for norfenfluramine. The AUC(0-t) at the NOAEL in this study, 9 mg/kg/day, provided a safety factor (both sexes combined) of approximately 3-fold or higher for fenfluramine and approximately 6-fold or higher for norfenfluramine.

Further preclinical data on ZX008 are available in the Investigator's Brochure (ZX008 IB).

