Study 1504 Cohort 2 required STP as a concomitant medication. Although the dose of ZX008 in Study 1504 Cohort 2 was lower than the high dose in Study 1, fenfluramine AUC0-24 values were approximately 130% higher in Study 1504 Cohort 2, than the high dose in Study 1, and norfenfluramine AUC0-24 values were approximately 60% lower than in Study 1. However, the clinical results indicated that the efficacy and AE profile were similar between Study 1 and Study 1504, indicating that the dose adjustment studied for the concomitant use of the STP regimen met the intended clinical outcome.

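### Section 5.4.1 makes the stiripentol dose limit both absolute and open to exception; separately, the 3-fold fenfluramine safety factor in Section 1.4 does not describe subjects on stiripentol

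*Protocol*

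**What the plan says.** **Dose limit with STP.** Section 5.4.1 sets the steps for subjects on STP: "the final dose change will be to 0.5 mg/kg/day, but not to exceed 20 mg/day". For early escalation after clinical worsening it repeats these figures and adds that "the maximal dose determined for subjects on concomitant STP must not be exceeded". The following sentence reads "Dosing outside of the specified range (ie, 0.2 to 0.8 mg/kg/day or 0.5 mg/kg/day for subjects taking concomitant STP) may be considered", subject to consultation between investigator and Medical Monitor. Earlier in the same section, adjustments outside the stated parameters are to be discussed with the Medical Monitor beforehand.

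Section 3.1 has the consultation sentence, with the STP limit named, but not the absolute bar. The synopsis has a shorter version: "Dosing outside of the specified range (ie, 0.2 to 0.8 mg/kg/day) may be considered after consultation between the investigator and Medical Monitor". Section 5.1 lists the doses to be studied as 0.2, 0.4, 0.6 and 0.8 mg/kg/day, "divided into two daily doses, up to a maximum of 30 mg/day".

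**Safety factor.** Section 1.4 says that exposure at the no-observed-adverse-effect level (NOAEL) in juvenile rats "provided a safety factor (both sexes combined) of approximately 3-fold or higher for fenfluramine", and about 6-fold or higher for norfenfluramine. It does not say which human exposure is the denominator. Section 1.5 reports that with STP, at the lower dose used there, fenfluramine AUC "values were approximately 130% higher in Study 1504 Cohort 2, than the high dose in Study 1", and that norfenfluramine AUC was about 60% lower.

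**The concern.** There are two separate defects.

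The first is operational. Adjacent sentences of the dosing section give a bar without exception and then a route past it. If a site and the Medical Monitor agree on a dose above the STP limit, a monitor or ethics committee cannot tell from the protocol whether that is permitted dosing or a deviation. The rule governs maximum exposure in the group that, by Section 1.5, had higher fenfluramine exposure at 0.5 mg/kg/day than subjects without STP had at 0.8 mg/kg/day.

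The second is descriptive. One unqualified fenfluramine margin is given for a trial that enrols subjects both with and without STP, and the protocol's own exposure figures show that it cannot apply to both.

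**Working it through.** **1. The dose-limit passages side by side**

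| Place | STP limit stated in that text | Can it be passed? |
|---|---|---|
| 5.4.1, early escalation | 0.5 mg/kg/day, 20 mg/day | No |
| 5.4.1, next sentence | 0.5 mg/kg/day | Yes, after consultation |
| 5.4.1, general adjustment rule | 0.5 mg/kg/day, 20 mg/day | Yes, after discussion |
| 3.1, early escalation | 0.5 mg/kg/day, 20 mg/day | Yes, after consultation |
| Synopsis, sentence before the range | 0.5 mg/kg/day, 20 mg/day | Not addressed |
| Synopsis, range sentence | None; range is 0.2 to 0.8 mg/kg/day | Yes, after consultation |
| 5.1, dose list | None; up to 0.8 mg/kg/day, 30 mg/day | Not addressed |

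The figures of 0.5 mg/kg/day and 20 mg/day agree wherever an STP limit is stated in full. What conflicts is the status of the limit: absolute in one sentence, variable in the others.

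**2. Reproducing the safety factor**

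Factor = mean of male and female NOAEL AUC ÷ human AUC over 24 hours.

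Inputs:
- NOAEL AUC (Section 1.4): fenfluramine 3480 (male) and 4680 (female); norfenfluramine 4470 and 6210 hr·ng/mL.
- Human AUC without STP (Table 3): fenfluramine 375 at 0.2 and 1390 at 0.8 mg/kg/day; norfenfluramine 220 and 872 ng·hr/mL.

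Means: fenfluramine (3480 + 4680)/2 = 4080; norfenfluramine (4470 + 6210)/2 = 5340.

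- Against 0.8 mg/kg/day without STP: 4080/1390 = 2.94 and 5340/872 = 6.12. These match the stated 3 and 6.
- Against 0.2 mg/kg/day without STP: 4080/375 = 10.9 and 5340/220 = 24.3. No match.

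**3. The same factor at 0.5 mg/kg/day with STP**

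- Fenfluramine, the stated increase taken literally: 1390 × 2.3 = 3197; 4080/3197 = 1.28 (males 3480/3197 = 1.09, females 4680/3197 = 1.46). If the true increase lay between 120% and 140%, the factor would be 1.33 to 1.22.
- Fenfluramine, if 130% higher was meant as 130% of: 1390 × 1.3 = 1807; 4080/1807 = 2.26.
- Norfenfluramine, 60% lower: 872 × 0.4 = 348.8; 5340/348.8 = 15.3.

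Neither fenfluramine reading gives 3. The norfenfluramine margin widens.

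**4. Extrapolation only**

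At 0.8 mg/kg/day with STP, assuming linear kinetics and an unchanged interaction, fenfluramine AUC would be 3197 × 1.6 = 5115 and the factor 0.80 (on the milder reading 1807 × 1.6 = 2891 and 1.41). The protocol reports no exposure data at that dose with STP.

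**The case against.** The strongest defence on dosing is that the Medical Monitor controls every departure. The synopsis, Section 3.1 and Section 5.4.1 all send adjustments outside the parameters to the Medical Monitor, Section 1.10 makes that discussion mandatory, and early escalation itself requires consultation. This stands to the extent that, read whole, the protocol does not let a site pass the STP limit alone. It does not remove the conflict. Under the absolute bar the Medical Monitor has no exception to grant; under the next sentence there is one.

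A reader might infer from the synopsis range that 0.8 mg/kg/day is a permitted STP ceiling. The documents do not support that. The preceding synopsis sentence gives 0.5 mg/kg/day and 20 mg/day, Sections 3.1 and 5.4.1 agree, and the STP taper in Table 6 has no row above 0.5 mg/kg/day and notes a 20 mg maximum. The range sentence is an omission. Section 5.1 is a product description, so its gap is also editorial.

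A reader might also infer that the 3-fold factor is lost because the dose limits conflict. It is not. It already fails at 0.5 mg/kg/day with STP, which every statement of the STP limit allows, and reconciling the limits would not restore it.

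Two further inferences should be resisted. Section 1.10 does not cite the rat margin; its case rests on clinical data, including Study 1504 Cohort 2, and Section 1.5 reports a similar adverse event profile there despite the higher fenfluramine exposure. Nor is this a cardiac margin: Section 1.4 reports no aortic or mitral valve histopathology in the juvenile rats, and the dose-related cardiotoxicity noted in Section 1.10 concerns adults.

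**Conclusion.** Both defects hold, independently of each other.

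The contradiction in Section 5.4.1 rests on no assumption; it is on the page. Its extent is one unresolved question, whether the STP limit may be varied with the Medical Monitor's agreement, plus two places where the limit is left out. Because it concerns the maximum dose, it should be corrected.

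The fenfluramine factor is wrong as a statement about subjects on STP: about 1.3 rather than 3, or about 2.3 on the mildest reading. It is a background figure and matters less. The result assumes that the unnamed human reference is 0.8 mg/kg/day without STP, which is inferred because only that exposure reproduces both stated factors, and that the Section 1.5 percentages apply to the Table 3 geometric means.

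No conclusion is drawn for 0.8 mg/kg/day with STP. The proportionality statement in Section 1.6 does not mention STP, and it describes 15 to 120 mg/day as a 4-fold range although 120/15 = 8, so it is weak support for scaling. No view is taken on which dose rule is right.

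**What to change.** 1. Reconcile the synopsis, Section 3.1, Section 5.1 and both parts of Section 5.4.1 into one statement for subjects on STP. It should give the limit in mg/kg/day and mg/day and say either that it is absolute or that it may be varied after Medical Monitor consultation. Use the same words in every place. The sponsor's clinical team decides which.
2. In Section 1.4, name the human exposure behind the safety factors and give the fenfluramine and norfenfluramine factors separately with and without STP.
3. In Section 1.5, replace the percentage comparison with the AUC values for Study 1504 Cohort 2, or make clear whether 130% higher means 2.3 times or 1.3 times.

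The cost is protocol wording in four places and a background paragraph, with one less favourable figure for fenfluramine and one more favourable for norfenfluramine. No new data, visits or procedures are needed.
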